2. Is this a multi-center study where the Penn IRB will be asked to serve as the IRB of Record for other external study sites?

No

Other Sites

No other sites

Protocol

Abstract

Cardiovascular disease is the leading cause of death in the US. While prevention approaches have improved longevity of patients, risk factors and adverse health behaviors (e.g., physical inactivity, smoking) are highly prevalent. The logistics and practicalities of meeting the goal of ideal CV health have not been clearly elucidated. Practice guidelines recommend using the Framingham risk score (FRS) or other risk prediction tools to classify patients risk of CV disease. These models however are imprecise and there is increasing focus on identifying markers that provide better measures of risk. As digital platforms are increasingly used to document lifestyle and health behaviors, data from digital sources may provide a window into manifestations of novel risk factors and potentially a better characterization of existing risk factors.

Objectives

Overall objectives

This study has three main objectives. (1) Identify and characterize topics and features derived from digital data (e.g., social media, online search, mobile media) which are associated with CHD and related risk factors and develop phenotypes of how patients use and engage with social media and then determine the association of these phenotypes with health status, social media perceptions, and patient activation. (2) Quantify and validate the incremental benefit of adding variables from patients' digital data to conventionally-derived predictive models of CHD (e.g. Framingham risk score/American College of Cardiology ASCVD Risk Estimator Plus) using a retrospective cohort of patients with and without heart disease. (3) In a cohort of patients with and without heart disease, develop and evaluate models that use digital media data to predict health care utilization (e.g. cost). (4) Evaluate the impact of dynamic health events (e.g. COVID-19) on modifiable CV health behaviors (smoking, diet, activity) using population level-digital media data (e.g. Facebook, Twitter)

Primary outcome variable(s)

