The primary outcome variable for the first objective will be topics and features (derived using the Latent Dirichlet Allocation [LDA] method for clustering language data) as well as a model-based approach of latent class analysis (LCA). We hypothesize: H1: There will be a difference in themes and topics posted by patients with heart disease and for patients without heart disease and use and engagement

phenotypes reflecting quantity, quality, and interaction of posts will be associated with health status, social media perceptions, and patient activation. The second objective outcome variable will be any CHD event. We hypothesize: H2: Adding digital data variables to conventionally-derived predictive models will improve the AUC for forecasting/predicting a CHD related event in a patient. The third objective outcome measure will be health care utilization measured by cost. We hypothesize: H3: Unique digital data variables identified for patients with heart disease and without heart disease will better predict future health care utilization costs for the health system. The fourth objective outcome measure will be the impact of dynamic health events on CV health behaviors. We have the following three hypotheses: H4,1: Digital media data will provide valid measures of health behaviors when compared with traditional sources. H4,2: Variations in digital data about modifiable CV health behaviors will correlate with dynamic health events. H4,3: Modifiable CV health behaviors (smoking, poor diet, and reduced physical activity) will increase more in response to dynamic health events in low income and minority communities.

Secondary outcome variable(s)

Given the correlational nature of this research the distinction between primary and secondary outcome variables is not particularly apparent.

Background

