
screener questions will be the same as the questions already built into our eligibility survey. If the patient is interested, they will receive a link to an eligibility survey to complete either over the phone with a team member or on their own time. The link will be sent via our secure shared Penn medicine email, MPM, or W2H on our HIPAA secure survey platform. If the patient is eligible and still interested, they will be asked to fill out a baseline survey at a time that works best for them. At that time, interested participants will be asked to complete the informed consent HIPAA authorization process at that time. The HIPAA authorization will also include detailed information about the request for permission to collect cost data. For example We are asking permission to collect information on your Medicare and/or insurance coverage and on your cost of care. This information will be collected directly from your insurance and medical record. Information will be collected for up to 5 years. If you agree to participate in this study the following information will be collected: type of health insurance, health insurance provider, health insurance policy, health insurance group number, and the policyholder's name and date of birth will be collected. If we aren't able to obtain your health insurance policy number, we will either call you to obtain your policy number or you can fill out a secure survey through REDcap that will allow you to input your policy number. For in-person enrollment, after the patient signs the informed consent the AA or CDH staff will complete the baseline survey and continue the enrollment process. Patients will complete several surveys on a research laptop (ThinkPad or MacBook air) and/or an iPad (e.g. NHANES: SES [income, education], diet behavior and nutrition, physical activity and physical fitness, smoking, and tobacco use; digital data use [Pew questionnaire]). For patients outside of UPHS, we will ask them to upload screenshots and/or self-report information from their office visit summaries, labs, vital signs, ED and inpatient hospital admission information since we will not have access to their EHR. For in-person enrollment, the survey will be collected on an incognito browser through either <https://donate.centerfordigitalhealth.upenn.edu> or REDcap. Once the survey is completed, the patient will reach a donate data page on the same browser, <https://donate.centerfordigitalhealth.upenn.edu> or be taking to another survey to share their digital data, <https://donate.centerfordigitalhealth.upenn.edu>, on one of the research laptops. For remote enrollment, participants will receive a link via email from our HIPAA secure survey platform to complete the baseline survey either on their own time or over the phone with a study team member. Interested participants will be asked to fill out a brief survey, via Redcap, asking what days and times work best for them to set-up a phone call with one of our team members to go over what is involved in participating in the study. They can either complete the enrollment process on the phone with the team member or on their own time. Subjects who meet case or control criteria, complete the consent process, and opt to share their social media data with the research team, will be instructed on how to share this information by logging into apps for Facebook and Instagram that have been created solely for the purpose of research. They will first be asked to create an account on our secure digital data platform/application (<https://donate.centerfordigitalhealth.upenn.edu>). Once they have confirmed information in the data collection survey, they will be directed to a Facebook application called Penn Image Station that was designed for the purposes of this study. The Penn Image Station application will gather information from their Facebook public profile, status updates, personal description, and likes. The application will not affect their usual use of Facebook nor will it post on their page. Facebook data will be collected prospectively for 60 days. If the participant shares their Instagram posts, they will be directed to an Instagram application called Penn Social Mediome. They will read a brief statement, either agree or disagree with the statement, and then log on to their Instagram account. Their Instagram posts and photos will be extracted by the Penn Social Mediome application and will be collected for 60 days prospectively. If our data collection application is not working, there will be a back-up plan set in place. We will ask participants to share their Instagram usernames so we to pull data manually from their account. If there are technological difficulties with our data collection application, we will reach out to participants at a later time to share their Instagram and Facebook data through the participants unique data sharing url. If there are technical difficulties with our application pulling Facebook data, we will ask participants to manually download a file of their Facebook data from their account. No passwords would be collected by the study team. If the patient has Twitter or Reddit accounts and wish to share that data as well, they will be asked to provide their Twitter handle (username) and/or Reddit handle (username). The participants IP addresses from their devices will be collected. If subjects opt and consent to share Google take-out information with us, they will download a zip file of their google searches and YouTube activity. Google take-out data is only retrospective. They will upload the zip file to the browser <https://donate.centerfordigitalhealth.upenn.edu>. If subjects opt and consent to share step tracking data with our research team and the patient is eligible and has Apple Health, S Health, Garmin, or Fitbit, they will export the data from the specific step tracking platform and the patient will upload this data to <https://donate.centerfordigitalhealth.upenn.edu>. Data collection manual outlines all data extraction procedures [See Appendix]. Data extracted from Facebook will include: age, gender,

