
some patients and not others. As the dependent variable will be cost, we will be attentive to informative censoring and right skewness, potentially using generalized linear models under a gamma distribution and log link. To account for informative censoring we will use inverse probability of censoring weighting. We will also explore the application of our new nested g-computation approach that allows for informative censoring and time- varying covariates to obtain future cost predictions. Additionally, we will generate summary statistics to describe the cohort and survey responses. We will use the model-based approach of latent class analysis (LCA)- to classify individuals into previously unmeasured subgroups. Variables to include in the LCA will include: demographics, years of platform use, posting: volume, quality, retransmission, and engagement. We will use the Bayesian information criterion to assess goodness of model fit, entropy to assess variations between classes, and the parametric bootstrapped likelihood ratio test to assess if a model with  $k$  classes has better performance than  $k-1$  classes. We will then use a regression model to compare with measures of health status, social media perceptions, and readiness/activation for each latent class. Models will be adjusted for demographics.

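### Objective 3 measures utilization by cost drawn from several payers and years, but the plan gives payer and price year no role, so an apparent digital gain could partly reflect price

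*Protocol*

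**What the plan says.** The protocol treats cost as a stand-in for utilization. Under Primary outcome variable(s): "The third objective outcome measure will be health care utilization measured by cost". H3, in the same section, adds a perspective and a direction in time: digital variables "will better predict future health care utilization costs for the health system".

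The source of the cost data appears once, in example authorization wording in the Design section: "We are asking permission to collect information on your Medicare and/or insurance coverage and on your cost of care", followed by "This information will be collected directly from your insurance and medical record" and "Information will be collected for up to 5 years". The insurance items listed there include "type of health insurance, health insurance provider, health insurance policy, health insurance group number". No cost metric is named: charge, allowed amount, paid amount and internal cost are all possible. The direction of the 5 years is not given either. Participants may be treated in other US health systems. For them the Design section says that the study has no access to the electronic record and relies on screenshots or self-report.

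The SAP (Final Analysis Plan, Objective 3), which repeats the protocol's Analysis Plan, says: "As the dependent variable will be cost, we will be attentive to informative censoring and right skewness". It proposes a possible gamma model with log link, inverse probability of censoring weights, GEE or mixed models for repeated measures, and Super Learner judged by cross-validated loss and calibration. It mentions no payer covariate, price year or price standardization for this objective.

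**The concern.** The amount recorded for a service depends on what was used and on the price attached to it. Prices can differ by payer and by year. If they do, and digital features are associated with payer, a model for cost can gain accuracy by recognising the payer. That gain would be read as support for H3, which concerns utilization.

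The protocol makes such an association plausible. It enrols ages 30-74 across Medicare and other insurance, and lists age, work history and education history among the extracted Facebook data.

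None of the planned methods removes a price multiplier. A gamma model with log link handles skewness, and censoring weights handle incomplete follow-up. Cross-validation guards against overfitting, but a payer-price signal recurs in the validation folds and is rewarded there as genuine prediction. Objective 2 has four nested models, including versions with socioeconomic status. Objective 3 names no base model, so nothing in the plan absorbs payer before the digital features are credited.

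**Working it through.** The documents give no alpha, power, effect size, cost variance or price ratio for H3, so there is no stated figure to reproduce. What follows is an illustration.

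**Inputs.** From the documents: several payers, up to 5 years of cost data (Design), and 1000 participants over 4 years (Study duration). Assumed: half the sample under each of two payers, price ratio 1.5 to 2.0, SD of log cost 1.5 at fixed prices, and a digital feature correlated r = 0.3 to 0.5 with payer and unrelated to utilization.

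**Spurious correlation with log cost.** On the log scale, cost is utilization plus price. With two equal payer groups, the SD of the price part is s = 0.5 x ln(ratio). The feature's correlation with log cost is rho = r x s / sqrt(1.5^2 + s^2).

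| Price ratio | s | r | rho | R-squared |
|---|---|---|---|---|
| 1.5 | 0.203 | 0.3 | 0.040 | 0.16% |
| 1.5 | 0.203 | 0.5 | 0.067 | 0.45% |
| 2.0 | 0.347 | 0.3 | 0.068 | 0.46% |
| 2.0 | 0.347 | 0.5 | 0.113 | 1.27% |

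Super Learner combines many features. If together they identified payer perfectly (r = 1), the ceiling under the same assumptions would be (0.203/1.514)^2 = 1.8% at ratio 1.5 and (0.347/1.540)^2 = 5.1% at ratio 2.0.

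**Check of the mechanism.** A simulation used the gamma model with log link at N = 1000, with 400 replicates per setting and cost CV from 1.0 to 2.0. Utilization was independent of both payer and a 50% binary marker. The share on the dearer payer differed between marker groups by 0.2 or 0.4. The table gives the percentage of runs in which the marker was significant at two-sided 0.05; ranges run over the CV values.

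| Price ratio | Gap 0.2 | Gap 0.4 |
|---|---|---|
| 1.5 | 8-23% | 25-69% |
| 2.0 | 17-48% | 53-97% |

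With one common price the figure was 3.5% to 6.5% in all settings, close to the nominal 5%. The artefact therefore comes from price and goes when price is removed.

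**Price year.** At an assumed 3% to 5% annual price growth, amounts 5 years apart differ by 1.03^5 = 1.16 to 1.05^5 = 1.28.

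**Why payer and year in both models helps.** If price depends only on insurance type and calendar year, it is constant within their combinations. A feature unrelated to utilization then has no remaining association with cost.

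**The case against.** Several stronger readings are tempting, and the documents do not support them.

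- *The SAP models raw insurer amounts.* It says only that the dependent variable is cost. The protocol names two sources, insurance and the medical record, and leaves the metric open. A data collection manual is cited as an appendix but is not among the documents reviewed.
- *H3's perspective contradicts its data source.* Only H3 adds the health-system qualifier, and it may mean health care generally. The wording is unclear rather than plainly contradictory, and the price problem remains on either reading.
- *Prices could drift over 9 years, by 1.30 to 1.55 at 3% to 5% a year.* This assumes that the 5 years run forward from each enrolment over a 4-year accrual, which is not stated, and it compares the extremes. If everyone had the same 5-year window, totals would differ by at most 1.03^4 = 1.13 to 1.05^4 = 1.22. The documents also tie no digital feature to calendar year, which a spurious association through drift would need.
- *Single-feature tests show a false positive.* The plan judges Objective 3 by cross-validated loss and calibration, so R-squared is nearer its scale, and there the effect is small. The simulation's CV range is also favourable to finding a signal: a log SD of 1.5 implies, for lognormal cost, a CV of sqrt(exp(2.25) - 1) = 2.9, which lies outside it.
- *All participants should be costed on one fee schedule.* That needs itemized service data, which the protocol does not promise for participants outside the Penn system. If the aim is to forecast actual spending, price is part of the target.

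What survives is narrower. The plan uses cost to represent utilization, collects insurance type, and gives it no place in the Objective 3 models.

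**Conclusion.** The point holds as a gap in the Objective 3 model, not as a demonstrated bias. Cost stands for utilization and comes from several payers over up to 5 years. The planned methods do not separate price from use, and no non-digital base model is defined. A positive H3 result could therefore partly reflect payer prices.

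The size cannot be determined from the documents. Under the stated assumptions one payer-marking feature would earn an R-squared of about 0.2% to 1.3%. That is small in absolute terms, but it could matter if the true digital gain is also small. The artefact needs both price differences by payer or year and digital features associated with payer or year; without either one it vanishes.

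**What to change.** In the SAP for Objective 3:

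1. Express costs in constant dollars of one stated year.
2. Define a non-digital base model that includes insurance type and calendar year. Keep both in the digital model, and judge H3 by the added cross-validated performance over that base.
3. State the cost metric, and the start and direction of the 5-year window.
4. Either limit H3's health-system claim to UPHS participants with UPHS cost records, or reword H3 to the perspective the data support.
5. Report price-standardized cost or utilization counts as a sensitivity analysis only, where itemized service data exist.

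The cost is SAP wording and slightly more data preparation, since insurance type is already collected. The digital gain may look smaller, because a feature that predicts utilization only through payer will earn no credit. Price differences within an insurance type would remain, and the sensitivity analysis would help to show whether they matter.
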